### 3.3.3. Data collection, surveys and follow-up:

The primary daily project management is carried out by the project manager. In addition, a project group (investigators), consisting of doctors from the departments involved, is trained to assist the project manager with the recruitment, sampling and follow-up of patients. All medical decisions regarding patients will be taken by a physician. Data is collected in Case Report Forms (CRF) for each individual patient.

Prior to consent to participate in the trial, we will only assess the specific information needed to assess inclusion and exclusion criteria. No other information will be accessed.

It is the attending physician who asks if patients are interested in hearing more about the trial. If yes, an investigator is contacted, who will inform the patient about the trial.

As part of the study, all patients will be regularly monitored for oxygen saturation, heart rate, blood pressure, respiratory rate and temperature during hospitalisation.

The following information will also be obtained:

- Date of birth, age and gender
- Height, weight and BMI
- Use of medicine
- For patients with chronic obstructive pulmonary disease (COPD) classification in GOLD 1-4 and GOLD A-D (symptoms assessed via MRC degree)
- Systematic screening for co-morbidities
- Smoking history with pack years, current smoking status and alcohol consumption
- Information from the chest x-ray
- Arterial-blood gas analysis (pH, pCO2, pO2, Base Excess, oxygen supplementation)
- Hb, leucocytes + differential count, CRP, kidney function, liver parameters, electrolytes, LDH
- ECG, vital status, and adverse events

And from the patients' medical journal:

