#### Secondary endpoints:

## Proactive Prophylaxis With Azithromycin and Chloroquine in Hospitalised Patients With COVID-19 (ProPAC-COVID)

Secondary endpoint no. 1:

Ordinate outcome. The patient is categorized into one of the following 8 categories on day 15:

1. Dead
2. Hospitalised and mechanical ventilation or ExtraCorporalMembraneOxygenation (ECMO)
3. Hospitalised and Non-invasive ventilation or high-flow oxygen device
4. Hospitalised and given oxygen supplements that do not live up to oxygen supplements in (2) or (3) - e.g. oxygen on nasal catheter
5. Hospitalised and do not receive oxygen supplementation but need treatment (COVID-19 related or other)
6. Hospitalised and do not receive oxygen supplements and do not need treatment (just observed)
7. Discharged with restriction on activities, may be free of oxygen depletion or use LTOT ("home oxygen")
8. Discharged, no restrictions on activities

Other secondary endpoints:

- Admitted to the intensive care unit in the two groups (0 vs. 1) during the index admission
  - o For patients admitted to intensive care unit: number of days on intensive care (Length of stay, ICU)
- Have been on Non-Invasive Ventilation (NIV) (0 vs. 1) during index hospitalisation
- Dead at day 30
- Duration (days) of index hospital admission
- Days alive and discharged from hospital within 30 days (summarises both whether the patient is alive and discharged from hospital)
- Dead at day 90 (reported later)
- Dead within 12 months (reported later)
- Number of readmissions for all causes within 30 days
- Number of days on NIV or mechanical ventilation during index admission
- Delta PaO2 day 1 (baseline) to day 4 (72 hours). At the same time oxygen supplements and oxygen systems are registered
- Delta PaCO2 day 1 (baseline) to day 4 (72 hours)
- pH day 4 (72 hours)

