## **DATA ANALYSIS**

### **Descriptive analyses – Baseline characteristics at study enrollment (defined as day 1).**

The following baseline characteristics of the study population will be summarized separately within each randomized group:

- Age, median (IQR), y
- Male sex, n (%)
- Ethnicity (Caucasian, African (incl. Afro-American), Asian, Inuit, Unknown/other)
- Body mass index ( $\text{kg}/\text{m}^2$ , median, IQR)
- Current smoker, n (%)
- Ex-smoker, n (%)
- Nonsmoker, n (%)
- Pack-years history (median, IQR, y)
- Use of oxygen therapy, n (%)
- Use of CPAP, n (%)
- Use of noninvasive mechanical ventilation, n (%)
- Infiltrate on Chest X-ray, n (%)
- Oxygen consumption: L/min (median, IQR)
- Oxygen consumption:  $\text{FiO}_2$  (median, IQR)

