### Biochemistry findings (daily measurements)

- Leukocyte count,  $\times 10^9$  cells/L
- Blood eosinophil count,  $\times 10^9$  cells/L
- CRP (mg/L)
- Fibrin D-dimer
- Ferritin
- Lactate Dehydrogenase (U/L)

### Arterial Blood Gas (mean $\pm$ SD) day 1 and day 4

- PCO2, mmHg
- PO2, mmHg
- HCO3
- pH

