7. Mortality [ Time Frame: 90 days] – reported in secondary publication.

Differences in mortality will be displayed using the Kaplan-Meier plots method in combination with the log-rank test and as an adjusted analysis using Cox proportional hazards models, while adjusting for the following variables: Age (per year increase), sex (M/F), COPD GOLD C/D (Yes vs. No), Heart failure NYHA III-IV (Yes vs. no), Active smoker (Yes vs. No).

8. Mortality [ Time Frame: 365 days] – reported in secondary publication.

Differences in mortality will be displayed using the Kaplan-Meier plots method in combination with the log-rank test and as an adjusted analysis using Cox proportional hazards models, while adjusting for the following variables: Age (per year increase), sex (M/F), COPD GOLD C/D (Yes vs. No), Heart failure NYHA III-IV (Yes vs. no), Active smoker (Yes vs. No).

9. Number of readmissions (all causes) [ Time Frame: 30 days]

Number of readmission and compared using a Mann-Whitney test, treating death as a competing risk.

10. Number of days using non-invasive ventilation (NIV) [ Time Frame: 14 days]

Number of days using non-invasive ventilation will be compared using t-test, treating death as a competing risk.

11. Change in patient's oxygen partial pressure [ Time Frame: 4 days ]

Delta PaO2 measured in arterial puncture

Changes will be calculated by an ANCOVA method adjusting for baseline values.

12. Change in patient's carbondioxid partial pressure [ Time Frame: 4 days ]

Delta PaCO2 measured in arterial puncture

Changes will be calculated by an ANCOVA method adjusting for baseline values.

13. Level of pH in blood [ Time Frame: 4 days ]

pH measured in arterial puncture

Levels in pH will be compared using t-test

14. Time to no oxygen supplement (or regular oxygen supplement "LTOT") [ Time Frame: 14 days]

Time to no oxygen supplement will be presented by the Kaplan-Meier method and differences calculated by log-rank test.

For all analyses using parametric statistic (t-test, ANCOVA) the distribution will be inspected. Biochemical markers will be transformed if necessary whereas length of stays will not be transformed. If parametric statistics is considered inappropriate a non-parametric alternative will be used. For analyses with a dichotomous outcome Fisher's exact test will be used if the chi-square test is not considered appropriate.

Arrhythmias:

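### Day-4 pH is compared by an unadjusted t-test although baseline pH is collected and PaO2 and PaCO2 are baseline-adjusted, so precision is lost

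*SAP*

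**What the plan says.** In the SAP, Secondary objective and outcomes, item 13 takes arterial pH with a four-day time frame and says "Levels in pH will be compared using t-test". No covariate is named. Items 11 and 12, immediately above, cover PaO2 and PaCO2, also from arterial puncture and over the same four days. For each the SAP says "Changes will be calculated by an ANCOVA method adjusting for baseline values".

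The protocol (section 3.3.5, Secondary endpoints) words the three endpoints differently. PaO2 and PaCO2 are changes, "day 1 (baseline) to day 4 (72 hours"), while pH is a level, "pH day 4 (72 hours").

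Baseline pH is available. Protocol section 3.3.3 lists it first in the blood gas panel: "Arterial-blood gas analysis (pH, pCO" and so on. The SAP tabulates the blood gas, pH included, under a heading that ends "SD) day 1 and day 4", and it equates baseline with day 1: "Baseline characteristics at study enrollment (defined as day 1").

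**The concern.** Three quantities come from one arterial blood gas. Two are adjusted for their day-1 value and the third is not, and the documents give no reason for the difference. If day-1 pH predicts day-4 pH within arms, the unadjusted comparison has a larger standard error and a wider confidence interval than the collected data allow. In any one randomisation it also passes on whatever baseline difference in pH chance has produced. At stake is the precision of one secondary outcome, not the validity of its test.

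**Working it through.** **Is adjustment planned anywhere else?** No. The SAP's covariate-adjusted models cover days alive and out of hospital (at 14 days, and at 30 days because item 6 is analysed in the same way) and mortality. None covers pH, and none uses baseline pH. The general rule after item 14 provides for inspection of the distribution, transformation of biochemical markers, and then "If parametric statistics is considered inappropriate a non-parametric alternative will be used". None of these brings in the baseline value.

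**The plan's own figure.** The documents give no power or sample size for pH. The only calculation is for the primary outcome (protocol section 3.3.6): difference 1.5 days, SD 4 days, two-sided 5%, power 80%.

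- Normal approximation: n per arm = 2 × (1.960 + 0.842)² × 4² / 1.5² ≈ 111.6, so 112 per arm, 224 in total.
- Exact t-test: 112.6, so 113 per arm, 226 in total, as stated.

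This reproduces the plan's number. It is used below only to set n = 113 per arm.

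**Variance with and without adjustment.** Let σ be the SD of day-4 pH within arm, ρ the within-arm correlation of day-1 with day-4 pH, and n the number per arm.

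- t-test on day-4 pH: Var = 2σ²/n
- ANCOVA with baseline pH: Var ≈ (2σ²/n) × (1 − ρ²) × [1 + 1/(2n − 4)]

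At n = 113 the last factor is 1 + 1/222 = 1.0045, the price of estimating one slope. The ratio of the two variances does not involve σ. ρ is not in the documents, so the values below are assumptions.

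The standard error falls by 1 − √(1 − ρ²). If the t-test has 80% power for some pH difference, ANCOVA has power Φ[(1.960 + 0.842)/√(1 − ρ²) − 1.960] for the same difference. These two columns leave out the factor 1.0045.

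| ρ (assumed) | 1 − ρ² | × 1.0045 | Fall in SE | Power when t-test has 80% | Simulated variance ratio |
|---|---|---|---|---|---|
| 0 | 1.00 | 1.0045 | 0% | 80.0% | 1.006 |
| 0.1 | 0.99 | 0.9945 | 0.5% | 80.4% | – |
| 0.3 | 0.91 | 0.9141 | 4.6% | 83.6% | 0.916 |
| 0.5 | 0.75 | 0.7534 | 13.4% | 89.9% | 0.753 |
| 0.6 | 0.64 | 0.6429 | 20.0% | 93.8% | – |
| 0.7 | 0.51 | 0.5123 | 28.6% | 97.5% | 0.503 |

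The simulation used 113 per arm and 4,000 runs for each ρ, and it agrees with the formula.

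**In patients.** At ρ = 0.5 the t-test needs 1/0.75 = 1.33 times the patients for equal precision. Equivalently, a t-test on 113 per arm is as precise as ANCOVA on about 113 × 0.75 ≈ 85 per arm.

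**Fewer day-4 gases.** The ratio hardly depends on n. At ρ = 0.5 it is 0.7551 with 75 per arm and 0.7578 with 50 per arm.

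**Level or change.** Regress day-4 pH on arm and baseline pH, then regress the change in pH on the same two terms. The second outcome is the first minus the covariate, so only the baseline coefficient shifts (by one) and the arm coefficient is identical. Adjustment therefore works for an endpoint defined as a level.

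**The case against.** The strongest reply is that the SAP follows the protocol: two endpoints are written as changes and one as a level, and the method differs accordingly. That explains the t-test but does not justify it, because ANCOVA on the day-4 level leaves the endpoint and the target mean difference as they are.

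Other points on that side stand in part:

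- **No bias.** Under randomisation the t-test is unbiased with correct type I error. This stands. Chance imbalance at baseline is already covered by its standard error, so carrying imbalance and losing precision are two views of one effect and should not be counted twice.
- **Unknown correlation.** This stands for the size of the gain. At ρ = 0.1 the variance falls by only about 1%. The downside is smaller still, at about 0.45% if ρ = 0.
- **No sample size rests on pH.** True. The factor of 1.33 is a measure of efficiency, not a recruitment consequence.
- **Missing day-1 gases.** A complete-case ANCOVA drops patients without a baseline value. Losing a fraction m multiplies the variance by 1/(1 − m), so the gain is cancelled when m reaches ρ²: 9% at ρ = 0.3, 25% at ρ = 0.5. The SAP reports the extent of missing data but has no imputation rule. Items 11 and 12 already depend on the baseline value in the same way.
- **Missing day-4 gases.** Absence through discharge or death may matter more for this endpoint, and baseline adjustment does not address it.

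**Conclusion.** The concern holds as a minor matter of efficiency and consistency. The textual facts are certain. The size is conditional: 9% to 36% lower variance for ρ between 0.3 and 0.6, close to nothing at ρ = 0.1, and a negligible cost at ρ = 0. It rests on three assumptions: a roughly linear relation between day-1 and day-4 pH, similar variability in the two arms, and day-1 values available for nearly all patients who have a day-4 gas. No conclusion on the primary outcome is affected.

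**What to change.** Replace the t-test in SAP item 13 with ANCOVA of day-4 pH on treatment arm and baseline pH, and report the adjusted mean difference with its 95% confidence interval. The protocol's endpoint wording can stay. The SAP's general rule on inspecting distributions already names ANCOVA, so that text need not change.

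It would help to add a sentence, applying to items 11 to 13 alike, on how a missing day-1 value is handled and how many patients contribute to each analysis.

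The cost is one line in the SAP, or two with the missing-baseline rule, and no new data or visits. The change should be dated before the outcome data are examined. Setting it before unblinding is not enough, because the SAP plans to run all analyses on coded arms before the randomisation code is broken.

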## Proactive Prophylaxis With Azithromycin and Chloroquine in Hospitalised Patients With COVID-19 (ProPAC-COVID)

- Neurogenic hearing loss
- Psoriasis
- Retinopathy
- Maculopathy
- Visual field changes
- Breastfeeding
- Severe liver diseases other than amoebiasis (spontaneous INR > 1.5)
- Severe gastrointestinal, neurological and hematological disorders (investigator-assessed)
- eGFR <45 ml/min/1.73 m^2
- Clinically significant cardiac conduction disorders/arrhythmias or prolonged QTc interval (QTc (f) of > 480/470 ms).
- Myasthenia gravis
- Treatment with digoxin\*
- Glucose-6-phosphate dehydrogenase deficiency
- Porphyria
- Hypoglycaemia (Blood glucose at any time since hospitalization of <3.0 mmol/L)
- Severe mental illness which significantly impedes cooperation
- Severe linguistic problems that significantly hinder cooperation
- Treatment with ergot alkaloids

\*The patient must not be treated with digoxin for the duration of the intervention. For atrial fibrillation/flutter, select according to the Cardiovascular National Treatment Guide (NBV): Calcium antagonist, Beta blocker, direct current (DC) conversion or amiodarone. In case of urgent need for digoxin treatment (contraindication for the aforementioned equal alternatives), the test drug should be paused, and ECG should be recorded daily.

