## Proactive Prophylaxis With Azithromycin and Chloroquine in Hospitalised Patients With COVID-19 (ProPAC-COVID)

\*The blood samples include haemoglobin (Hb), leukocytes + differential count, thrombocytes, C-reactive protein (CRP), Na+, K+, albumin, creatinine, urea, amylase, alkaline phosphatase, beta-2-Microglobulin, fibrinogen, glucose, TSH, INR, bilirubin, D-dimer, APTT, calcium, triglycerides, ferritin and lactate dehydrogenase (LDH). These blood tests will also be recommended daily for COVID patients outside studies in the recommendation of the Danish lung medicine association. \*\*When screening for the study, any ECG from within the last 3 days can be used. \*\*\*A follow-up ECG can be recorded during any remaining days of the hospital admission. \*\*\*\*Only in patients with COPD.

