### Regarding other treatment with antibiotics:

If antibiotic therapy is deemed indicated to the patient due to e.g. pneumonia or if it becomes standard therapy, piperacillin-tazobactam should be given as an empirical treatment at a dose adjusted to renal function. In case of penicillin allergy, cefuroxime is also given at a dose appropriate to renal function, weight and age. When positive microbiology is available, immediately switch to targeted treatment.

If *specific suspicion of atypical pneumonia* is raised, ciprofloxacin is administered at a dose of corresponding to kidney function and concomitant examination for atypical pneumonia will be performed. If negative, ciprofloxacin is discontinued. If positive, ciprofloxacin treatment is continued for the duration of treatment corresponding to the microorganism detected. If there is a specific need for treatment with macrolide and where other options are not available (e.g. allergy to fluoroquinolones, or when there is an estimated need for combination treatment of e.g. legionella pneumonia), consult with an investigator, and in this case it may be decided to discontinue azithromycin (active) or azithromycin placebo. In this case, treatment stops without unblinding.

Furthermore, ECG recordings during the treatment period will be analysed with focus on QTc. At QTc (F) > 480/470 ms for respectively women and men, IMP will be discontinued for safety reasons (but the patient remains in the study).

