### Other Lab findings

- QTc (F) (via electronic measurement on ECG at baseline)

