- ECG: Qtc: n (%) patients in both arms who at any time point after baseline had a QTc (F) >500 ms
- N (%) ventricular arrhythmias (apart from ventricular extrasystoles and non-sustained VT).

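### The only post-baseline QTc outcome (above 500 ms) lies 20 to 30 ms above the level at which study drug is stopped, and neither crossings of that level nor QTc stops are tabulated

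*SAP*

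**What the plan says.** In the SAP, the arrhythmia items at the end of Secondary objective and outcomes contain one QTc measure: "n (%) patients in both arms who at any time point after baseline had a QTc (F) >500 ms". The other item is a count of ventricular arrhythmias. QTc(F) also appears under Other Lab findings, but only at baseline, and as a baseline subgroup variable.

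The protocol (3.3.4, Regarding other treatment with antibiotics) states: "At QTc (F) > 480/470 ms for respectively women and men, IMP will be discontinued for safety reasons". It adds in parentheses, "but the patient remains in the study". The exclusion criteria use the same pair of values at entry. The same part of 3.3.4 says that "ECG recordings during the treatment period will be analysed with focus on QTc", without naming a measure.

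On ECG timing, the legible text is a footnote to the schedule: "A follow-up ECG can be recorded during any remaining days of the hospital admission". The schedule table itself cannot be read in the text available for this review, so the planned number of ECGs is unknown here.

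**The concern.** A patient whose QTc(F) passes 480 or 470 ms has met the trial's own criterion for stopping drug on safety grounds. If that patient's highest value is 500 ms or less, the planned QTc line records no event. The protocol lists QT prolongation as a known reaction to both drugs, and they are given together. A row with zero or one case per arm could be read as absence of a QT signal, while the number of patients who met the stopping criterion in each arm is nowhere shown.

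The timing matters because the SAP (Blinding of the statistician) allows no further analysis after unblinding except at the request of reviewers or editors. A measure not specified beforehand would be post hoc.

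**Working it through.** **1. Gap between the two levels.** Women: 500 − 480 = 20 ms. Men: 500 − 470 = 30 ms. Patients above 480/470 ms are excluded at entry, so a later crossing is new relative to the screening ECG.

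**2. Is the gap covered elsewhere?**
- SAP, Adherence data: patients who started and completed each drug, by arm. No reason for stopping.
- SAP, Other Lab findings: QTc(F) at baseline only.
- Protocol section 6: side effects already in the drug summary are not recorded. The protocol's own lists include QT prolongation for both drugs, so a non-serious rise need not enter the adverse-event data.
- Protocol 3.3.3: ECG is among the data collected. The list does not mention a reason for stopping drug.

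No planned table covers the gap.

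**3. The plan's own figure.** The documents give no rate, SD or effect for QTc. The only reproducible figure is the sample size. With a difference of 1.5 days, SD 4, two-sided 5% and 80% power, 2 × (1.960 + 0.842)² × 4² / 1.5² = 112 per arm after rounding up. The exact t-test gives 112.6, so 113 per arm, as stated. It is used below only as the number of patients per arm.

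**4. What a count above 500 ms can show with 113 per arm.** Expected cases = 113p; chance of none = (1 − p)^113.
- p = 1% (assumed): 1.1 cases; 0.99^113 = 32%.
- p = 2% (assumed): 2.3 cases; 0.98^113 = 10%.
- With 1% in control, 80% power needs about 9% in the active arm.

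**5. Illustration of the gap, with every QTc input assumed.** A simulation used baseline mean 430 to 435 ms, SD 20 to 25 ms, truncated at 470/480 ms; 60% men; mean drug effect 15 to 35 ms, complete by day 7; within-patient SD 10 to 15 ms; 30% of the effect remaining after a stop; and one, three or seven on-treatment ECGs.
- Active arm: 5 to 58% cross 470/480 ms; 0.1 to 8% exceed 500 ms.
- Crossers not counted: 81 to 99%.
- Difference between arms: 3 to 42 percentage points at 470/480 ms; 0.1 to 7 points above 500 ms.

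**6. Separating the cut-off from the stopping rule.** Take one scenario: mean 430, SD 20, effect 25, within-patient SD 10, ECGs on days 2, 4 and 7.
- Crossing 470/480 ms: 23.5% active and 3.4% control, or 113 × 0.235 = 26.6 and 113 × 0.034 = 3.8 patients.
- Above 500 ms with the stopping rule: 1.03% and 0.03%, or 1.2 and 0.03 patients.
- Above 500 ms in the active arm without the rule: 3.08%.
- A first crossing always precedes the stop, so 23.5% is the base in both cases. The cut-off alone leaves 1 − 3.08/23.5 = 87% of crossers uncounted; the rule raises this to 1 − 1.03/23.5 = 96%.
- Share of cases above 500 ms removed by the rule here: (3.08 − 1.03)/3.08 = 67%.

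Across scenarios this last share is about 0% with one ECG, 34 to 68% with three and 46 to 88% with seven. With a single ECG it must be zero, because no later reading can be affected.

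**The case against.** Above 500 ms is a legitimate severe-event count. It describes the regimen as given, stopping rule included, and the SAP does not present it as an estimate of the drugs' effect on QTc. Stopped patients stay in the study and the outcome counts any time after baseline, so a triggering ECG above 500 ms counts, as does a later one. Ventricular arrhythmias are reported separately. Serious reactions go to the sponsor even if listed in the product summary. The completion figures would show an excess of early stops in one arm. All of this stands. None of it tells the reader how many patients met the protocol's QTc criterion, or how many stops were for QTc.

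A reader might infer that the stopping rule hides most of the QT effect. The documents do not support that. Patients between 470/480 and 500 ms are left out by the cut-off itself, in both arms, with or without a stopping rule. The part due to stopping depends on how often ECGs are taken, which cannot be read here. Nor do the documents support a claim that drug would be stopped for QTc far more often in the active arm, since they give no QTc rate for either arm.

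**Conclusion.** The point holds as a reporting gap. The single post-baseline QTc measure lies above the trial's own stopping level, and nothing else in the plan counts patients in between. Patients stopped for QTc who peak at or below 500 ms are non-events in the table, so the QT effect is likely to be understated.

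That statement concerns numbers of patients and absolute differences. A ratio above 500 ms need not be smaller, but it would rest on very few cases. The size cannot be computed from the documents; the ranges above rest wholly on assumed QTc inputs and only show that the loss could be large. The fault is that the count above 500 ms stands alone, not that it is used. No judgement is made on which clinical threshold is right.

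**What to change.** Before unblinding, add to the SAP, by arm:

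- n (%) with a post-baseline QTc(F) above the protocol's 480/470 ms threshold, with the number of patients having at least one post-baseline ECG as denominator. Use the same denominator for the count above 500 ms.
- Change in QTc(F) from baseline to a comparable on-treatment ECG, for example the first follow-up ECG, adjusted for baseline, with 95% CI. The SAP already plans ANCOVA of this kind for blood gases. Avoid the maximum change: it grows with the number of ECGs, and follow-up ECGs are tied to remaining hospital days and so to length of stay. Any-time counts share this weakness to some degree, which is why the fixed comparison is needed beside them.
- n (%) with study drug stopped for QTc, if the CRF records the reason.

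Keep the count above 500 ms as the severe-event line.

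The cost is a few descriptive rows, not adjusted for multiplicity. The first two items need only ECG values, which the protocol already collects. The third may need a check of the CRF, because the documents do not show that stop reasons are recorded. No clinical rule changes.
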